19.5. Laboratory Measure Schedule

As available, local laboratory measures of platelet count, Hgb, white blood cell count, absolute neutrophil count, LDH, haptoglobin, creatinine, bilirubin, AST, ALT, alkaline phosphatase, and schistocytes will be collected according to the following schedule:

Pre-TMA period:

- Once immediately prior to conditioning
- On Day -1 or 0 prior to transplant (the measure closest to the transplant). (Day 0 is the day of transplant)
- On Days +2, +4, +6, +8, +10, +14, +21, +28 following transplant and weekly thereafter until 28 days prior to the diagnosis of TMA

TMA period:

- Daily from 28 days prior to the diagnosis of TMA to the later of 12 weeks following the diagnosis of TMA or 4 weeks following resolution of TMA

Post-TMA period:

- Once weekly following the TMA period for 4 weeks, then once every 2 weeks for 4 weeks, and then once monthly \pm 3 days until up to 2 years following the first dose of OMS721

Platelet count should be recorded immediately before and after each platelet transfusion.

Hemoglobin levels should be recorded immediately before and after each RBC transfusion.

Abbreviations: ALT = alanine aminotransferase; AST = aspartate aminotransferase; Hgb = hemoglobin; LDH = lactate dehydrogenase; RBC = red blood cell; TMA = TMA = thrombotic microangiopathy.

CONFIDENTIAL

No use, disclosure or reproduction outside of Omeros without prior written authorization

Table 2:	Example of Baseline Platelet Count Calculation	13
Table 3:	Analysis Visits for Data Collected at Scheduled Visits.....	13

LIST OF ABBREVIATIONS AND DEFINITION OF TERMS

Abbreviation or Specialist Term	Definition
AE	adverse event
aHUS	atypical hemolytic uremic syndrome
AUC	area-under-the-curve
CI	confidence interval
CTCAE	Common Terminology Criteria for Adverse Events
ECG	electrocardiogram
FAS	Full Analysis Set
GVHD	graft-versus-host disease
Hgb	hemoglobin
HSCT	hematopoietic stem cell transplant
HSCT-TMA	HSCT-associated thrombotic microangiopathy
IV	intravenous
LDH	lactate dehydrogenase
LLOQ	lower limit of quantitation
MAGIC	Mount Sinai Acute GVHD International Consortium
MASP-2	mannan-binding lectin-associated serine protease 2
MedDRA	Medical Dictionary for Regulatory Activities
NCI	National Cancer Institute
PAS	Per-protocol Analysis Set
PD	pharmacodynamic
PK	pharmacokinetic
RBC	red blood cell
RRT	renal replacement therapy
SAP	statistical analysis plan
SAE	serious adverse event
SOC	System Organ Class
TMA	thrombotic microangiopathy
TTP	thrombotic thrombocytopenic purpura
ULN	upper limit of normal

Within this Statistical Analysis Plan (SAP), narsoplimab is referred to as OMS721.

1. STUDY DESCRIPTION

1.1. Study Objectives

The purpose of this Phase 2 study is to evaluate the safety, efficacy, pharmacokinetics (PK), pharmacodynamics (PD), and immunogenicity of OMS721 in patients with thrombotic microangiopathies (TMA). As of Protocol Amendment 11, the primary and secondary endpoints are modified to provide for evaluation of response in patients with hematopoietic stem cell transplant (HSCT)-associated TMA.

The co-primary objectives of this study are to:

- Assess the safety and tolerability of multiple-dose administration of OMS721 in patients with TMA (this will be assessed in patients with HSCT-TMA as well as in patients with atypical hemolytic uremic syndrome [aHUS] or thrombotic thrombocytopenic purpura [TTP])
- Evaluate the efficacy of OMS721 in patients with HSCT-TMA by response defined as:
 - Improvement in TMA laboratory markers of platelet count and lactate dehydrogenase (LDH), and
 - Improvement in clinical status

The secondary objectives of this study are to evaluate the following in patients with HSCT-TMA treated with OMS721:

- Duration of response
- 100-day survival
- Overall survival (OS)
- Renal function in patients who had renal dysfunction at baseline
- Platelet count change from baseline
- Lactate dehydrogenase change from baseline
- Haptoglobin change from baseline
- Hemoglobin (Hgb) change from baseline
- Creatinine change from baseline in patients who had no reason other than HSCT-TMA for creatinine elevation
- Freedom from platelet transfusion in patients who received at least 1 platelet transfusion within 2 weeks of the first OMS721 dose
- Freedom from red blood cell (RBC) transfusion in patients who received at least 1 RBC transfusion within 2 weeks of the first OMS721 dose
- The PK of multiple-dose administration of OMS721 (this will be assessed in patients with HSCT-TMA as well as patients with aHUS and TTP)

- The PD of multiple-dose administration of OMS721 (this will be assessed in patients with HSCT-TMA as well as patients with aHUS and TTP)
- The immunogenicity of multiple-dose administration of OMS721 (this will be assessed in patients with HSCT-TMA as well as patients with aHUS and TTP)

The exploratory objectives of this study are to:

- Assess the effect of baseline circulating mannan-binding lectin (MBL) levels on PK and PD measures
- Assess the effect of baseline circulating mannan-binding lectin-associated serine protease 2 (MASP-2) levels on PK and PD measures
- Describe the effect of OMS721 on TMA laboratory markers in patients with aHUS and TTP

1.2. Study Design

This is a Phase 2, uncontrolled, three-stage, ascending-dose-escalation study in patients with TMA: aHUS, TTP, or HSCT-TMA. As originally designed, the primary outcomes to be measured were safety and clinical activity. The secondary outcomes to be measured were PK, PD, and immunogenicity (i.e., presence of anti-drug antibody [ADA] response). Amendment [REDACTED] discontinued enrollment of patients with aHUS and TTP. Amendment [REDACTED] provides for collection of additional data from patients with HSCT-TMA, changes the primary and secondary objectives to focus on HSCT-TMA, and defines criteria by which to determine clinical response to treatment. Amendment 11 also provides for collection of PK and PD measures for analysis within integrated population PK and PD analyses across different studies.

In Stage 1 of the study, OMS721 was administered to 3 cohorts (Cohorts 1, 2, and 3), with dose escalation by cohort to identify the optimal dosing regimen. After enrollment and treatment of each cohort, there was a safety review to determine whether dose escalation should proceed. In Stage 2, the dose selected in the first stage was administered to expanded cohorts initially planned to be 40 patients per cohort with distinct etiologies (aHUS alone in 1 cohort, and TTP or HSCT-TMA in the other cohort). As of Amendment 10 of the protocol, enrollment of aHUS and TTP patients was closed.

Each patient in Stage 1 received 4 weekly doses of OMS721. Prior to Amendment 10, patients in Stage 2 with aHUS received 12 weekly doses and patients with TTP or HSCT-TMA received 4 weekly doses, and Stage 3 allowed for additional treatment based upon the patient's response to therapy. As of Amendment 11 of the protocol, Stage 1 is complete.

OMS721 will be administered by intravenous (IV) infusion. The planned enrollment is up to approximately 60 patients overall. The stages, cohorts, and treatments are provided in [Table 1](#).

Table 1: OMS721-TMA-001 Treatment Stages and Cohorts

Cohort and (Stage)	Number of Patients			OMS721 Dose
	aHUS	TTP	HSCT-TMA	
1 (Stage 1)	3	0	0	0.675 mg/kg weekly x 4
2 (Stage 1)	2	1	0	2.0 mg/kg weekly x 4
3 (Stage 1)	2	0	2	4.0 mg/kg weekly x 4
4 (aHUS only) (Stage 2 and 3)	14	0	0	4.0 mg/kg weekly x 12 for each Stage
	4	0	0	400 mg weekly x 12
5 (TTP or HSCT-TMA) (Stage 2 and 3)	0	4	22	4.0 mg/kg weekly x 4 for each Stage
5 (TTP or HSCT-TMA) (Stage 2 and 3)	0	0	4	370 mg weekly x 4 for each Stage

aHUS = atypical hemolytic uremic syndrome; HSCT-TMA = hematopoietic stem cell transplant-associated thrombotic microangiopathy; TTP = thrombotic thrombocytopenic purpura

For patients with HSCT-TMA enrolled under Amendment [REDACTED] or under earlier versions of this protocol, additional data will be collected. Notification and consent of patients (or legal representatives for deceased patients) for this additional data collection will be performed as needed according to local rules and regulations.

These additional data are outlined in Protocol Amendment [REDACTED]. These data will include supplemental data on patient demographics and baseline conditions, donor characteristics, the transplant procedure, concomitant medications, TMA-related laboratory measures, transfusions, transplant complications, and outcomes. Details of these data are provided in Appendix 1 of the protocol amendment. These data will be derived from medical records from the time of transplant conditioning through the last available patient contact with the site or 2 years (104 weeks) after the first OMS721 dose, whichever is earlier. These data were requested by regulatory authorities because patients who have undergone HSCT typically have complicated post-transplant courses and these additional data will allow for better understanding of OMS721 response and outcomes. As of Amendment 11, enrollment in the study has been completed, and the additional data will be collected until a predetermined data cutoff date for those patients who have not reached 2 years after first OMS721 dose.

1.3. Determination of Sample Size

In Stage 1, 3 patients per dose escalation cohort is a common scheme and is considered to be sufficient in combination with data from the Phase 1 study to allow selection of a dose for Stage 2.

In stage 2, the sample size for each cohort (aHUS, and HSCT-TMA/TTP) is determined by comparison to the total sample size of uncontrolled Phase 2 studies that provided sufficient data for approval of eculizumab for the treatment of aHUS [Legendre 2013]. This sample size is considered adequate in these orphan diseases to identify treatment effects in uncontrolled studies.

It is expected that approximately 28 HSCT-TMA patients enrolled before Protocol Amendment [REDACTED] will be included to support a regulatory approval. The width of the exact 95% confidence interval (CI) for the response rate based on 28 HSCT-TMA patients ranges from 12.3% to 38.7%. If the observed response rate is 50%, the exact 95% CI is 30.6% to 69.4%.

2. STATISTICAL METHODS

2.1. Study Endpoints

The co-primary endpoints are:

- Safety as assessed by adverse events (AE)s, vital signs, electrocardiograms (ECG)s, and clinical laboratory tests (includes patients with HSCT-TMA, aHUS, and TTP)
- For HSCT-TMA patients, response to OMS721 treatment. A responder is defined as a patient with HSCT-TMA who demonstrates improvement in laboratory TMA markers (platelet count and LDH) and clinical benefit (either improvement in organ function or reduction in transfusion burden). The specific criteria are defined as follows:
 - Improvement in laboratory TMA markers:
 - Platelet count:
 - For patients with baseline platelet count $\leq 20,000/\mu\text{L}$:
 - Tripling of baseline platelet count
and
 - Post-baseline platelet count $> 30,000/\mu\text{L}$
and
 - No platelet transfusions 2 days before and on the day of the platelet count collection
 - For patients with baseline platelet count $> 20,000/\mu\text{L}$
 - Increase in platelet count $\geq 50\%$
and
 - Post-baseline platelet count $> 75,000/\mu\text{L}$
and
 - No platelet transfusions 2 days before and on the day of the platelet count collection
 - and
 - LDH:
 - LDH < 1.5 x upper limit of normal (ULN)

and

- Improvement in clinical status:
 - Improvement in organ function as evidenced by any of the following:
 - Improvement in renal function:
 - Reduction of creatinine > 40%
 - or
 - Creatinine < ULN and reduction of creatinine > 20%
 - or
 - Discontinuation of renal replacement therapy (RRT),
 - or**
 - Improvement in pulmonary function:
 - Extubation and discontinuation of ventilator support
 - or
 - Discontinuation of non-invasive mechanical ventilation (continuous positive pressure ventilation)
 - or**
 - Improvement in neurological function:
 - Improvement in reversible neurological conditions (e.g., cessation of seizures)
 - or
 - Stabilization of irreversible neurological conditions (e.g., stability of neurological deficits following stroke without further deterioration or subsequent strokes)
 - or**
 - Improvement in gastrointestinal function (gastrointestinal HSCT-TMA will require diagnosis by tissue biopsy):
 - Improvement measured by improvement in the gastrointestinal measures in the Mount Sinai Acute GVHD International Consortium (MAGIC) criteria
 - or**
 - Freedom from transfusion (no transfusions for at least 4 weeks from the last transfusion except for patients who died within 4 weeks of the last transfusion, only evaluated in patients who received transfusions within the 2 weeks prior to or on the first OMS721 dose date).

The secondary endpoints of this study are to evaluate the following in patients with HSCT-TMA treated with OMS721:

- Duration of response defined as the number of days from the first response date to the first relapse date
- 100-day survival, from the date of TMA diagnosis
- Overall survival, from the date of TMA diagnosis
- Freedom from platelet transfusion defined as no platelet transfusions for at least 4 weeks following the last platelet transfusion except for patients who died within 4 weeks of the last platelet transfusion (only evaluated in patients who had platelet transfusions in the 2 weeks prior to or on the first OMS721 dose date)
- Freedom from RBC transfusion defined as no RBC transfusions for at least 4 weeks following the last RBC transfusion except for patients who died within 4 weeks of the last RBC transfusion (only evaluated in patients who had RBC transfusions in the 2 weeks prior to or on the first OMS721 dose date)
- Change from baseline in platelet count (post-baseline platelet counts without platelet transfusions 2 days before and on the day of the platelet count collection will be used) over time using central laboratory values
- Change from baseline in LDH over time using central laboratory values
- Change from baseline in haptoglobin over time using central laboratory values
- Change from baseline in Hgb (post-baseline Hgb without RBC and whole blood transfusions 6 days before and on the day of the Hgb collection will be used) over time using central laboratory values
- Change from baseline in creatinine over time using central laboratory values

2.2. Analysis Populations

Efficacy analyses will be performed for the Full Analysis Set (FAS) population and the Per-protocol Patient Set (PAS) population. The FAS population will include all HSCT-TMA patients

who received any amount of study drug. The PAS population will include all HSCT-TMA patients who received at least 4 weeks of study treatment (treatment period is greater than or equal to 28 days).

Safety analyses will be based on the Safety Analysis Set population, which includes all patients (aHUS, TTP, and HSCT-TMA) who received any amount of study drug.

The Enrolled population is defined as all patients who completed the informed consent.

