10.1.1.7. Stage 1 Treatment – Week 4 (Visit 5, Day 22 ± 1)

This is the fourth and last dose of OMS721 administration. The following procedures will be performed:

1. AEs, presence of TMA symptoms, concomitant medications, and therapies will be recorded.
2. Vital signs will be taken, including BP, pulse rate, RR, and temperature (after at least 5 minutes of rest in the supine position) at the following time points: prior to dosing and at 15 minutes, 30 minutes, 1 hour, and 2.5 hours after start of dosing.
3. ECG will be taken (after at least 5 minutes of rest in the supine position) prior to dosing.
4. Clinical laboratory tests will be performed for hematology, chemistry, LDH, haptoglobin, coagulation, and urinalysis (prior to OMS721 administration).
5. Blood sample for future research related to TMA will be taken (prior to OMS721 administration).
6. OMS721 will be administered by IV infusion over approximately 30 minutes.
7. ECG will be taken (after at least 5 minutes of rest in the supine position) immediately before the 5 minute PK sample.
8. Serum PK samples will be taken prior to dosing and at the following time points after end of dosing: 5 minutes, 2 hours, 24 hours (Day 23), 48 hours (Day 24), 72 hours (Day 25).
9. Serum PD samples will be taken at the following time points: prior to dosing and at 2 hours after end of dosing.
10. Serum ADA sample will be taken prior to dosing.
11. AEs during and after the IV infusion will be recorded.

CONFIDENTIAL

No use, disclosure or reproduction outside of Omeros without prior written authorization

12. Arrangements should be made for the patient to undergo collection of PK samples on the 3 days following Visit 4 (Day 23, Day 24, and Day 25 if Visit 4 occurs on Day 22).

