10.1.6. Timing of Study Visits

Visits outside the specified window will be considered protocol deviations. If OMS721 is not able to be administered within the visit window ± 2 days, the Investigator should contact the Sponsor Medical Monitor to discuss the course of action and disposition of the patient.

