13.2.1.2. Analysis Populations

Efficacy analyses will be performed for the Full Analysis Set (FAS) population and the Per-protocol Patient Set (PAS) population. The FAS population will include all HSCT-TMA patients who received any amount of study drug. The PAS population will include all HSCT-TMA patients who received at least 4 weeks of study treatment (treatment period is ≥ 28 days).

Safety analyses will be based on the Safety Analysis Set population, which includes all patients (aHUS, TTP, and HSCT-TMA) who received any amount of study drug.

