2.4. Study Day and Treatment Period

Study day is defined as

- Event Date – First Dose Date + 1 if the event date is on or after the first dose date
- Event Date – First Dose Date if the event date is before the first dose date

Study Day 1 is defined as the first dose date.

Treatment period is defined as the number of days from the first dose date to the last dose date + 7. The duration of treatment is defined as last dose date + 7 – first dose date + 1.

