2.8.2. Efficacy Analyses

2.8.2.1. Primary Efficacy Endpoint

A patient is a responder if this patient meets the responder criteria (Section 2.1) at any time post-baseline during the study. If a patient is not evaluable for a response criterion due to confounding factors, the non-evaluable response criterion will not be included in the determination of responder. Evaluability of each response criterion will be determined by a clinical review of relevant data and will be documented in the clinical study report. For example, potential confounding factors include graft failure for platelet count or transfusions, and nephrotoxic medications for renal function. Furthermore, laboratory values collected from both the local laboratories and the central laboratories will be used to determine response status.

Analysis of the primary efficacy endpoint will use a non-responder imputation to impute missing or incomplete data to evaluate response. The number and percent of responders will be summarized with exact 95% CI (Clopper-Pearson) by dose and total for the FAS and PAS

populations. If the lower bound of the exact 95% CI is greater than 15%, there is sufficient evidence to demonstrate efficacy of narsoplimab in the target patient population. Each criteria of the response will be listed for each patient.

Sensitivity analyses will include:

1. Subgroup analyses for the following subgroups will be performed for the FAS population:
 - Age (< 65 , ≥ 65 years)
 - Gender (Male or Female)
 - Graft-versus-host disease (GVHD) (Yes or No)
 - Significant infection (Yes or No)
 - Graft failure or non-engraftment (Yes or No)
 - Female-to-male transplant (Yes or No)
 - Multiple organ TMA involvement (Yes or No)
 - Mismatched donor (Yes or No)
 - Baseline platelet counts ($< 20,000$ or $\geq 20,000$ platelets/ μL)
 - Renal dysfunction at baseline (Creatinine $> \text{ULN}$ or spot urine protein $\geq 2+$ or > 30 mg/dL; Yes or No)
 - Any transfusions within the 2 weeks prior to or on the first OMS721 dose date (Yes or No)
2. A completer analysis will be performed using the patients with non-missing responses only. Exact 95% CI for the completer response rate will be provided for the FAS population by dose.
3. Two alternative definitions of response will be analyzed:

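### The per-protocol set is defined by a 28-day span with no dose count, so it can include a patient given two of four doses and exclude one given three

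*SAP*

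**What the plan says.** SAP section 2.2 limits the PAS to HSCT-TMA "patients who received at least 4 weeks of study treatment (treatment period is greater than or equal to 28 days". Protocol section 13.2.1.2 agrees: "received at least 4 weeks of study treatment (treatment period is ≥ 28 days". Neither adds a dose count, a dose-intensity threshold or a deviation criterion, and SAP section 2.3 places protocol deviations outside the SAP.

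SAP section 2.4 then gives two measures. The first is the term used in the PAS rule: "Treatment period is defined as the number of days from the first dose date to the last dose date + 7". The second is one day longer: "The duration of treatment is defined as last dose date + 7 – first dose date + 1". SAP section 3.2.2.2 uses the second for the exposure summary, including an optional count of patients treated for at least 4 weeks.

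On the schedule, SAP section 1.2 says that "patients with TTP or HSCT-TMA received 4 weekly doses" in Stage 2, and protocol section 19.3 places these on Days 1, 8, 15 and 22. For Stage 1 the fourth dose has a printed window, "Week 4 (Visit 5, Day 22 ± 1". No per-visit window is printed for Stage 2 or 3. Protocol section 10.1.6 has a general sentence beginning "If OMS721 is not able to be administered within the visit window ± 2 days", which then tells the investigator to contact the medical monitor.

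SAP section 2.8.2.1 reports the primary responder rate, with its exact confidence interval, for both the full analysis set (FAS) and the PAS.

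**The concern.** A per-protocol set is meant to show whether the result holds among patients treated as planned. Here only the first and last dose dates decide membership, and whatever happens between them is ignored. The set can therefore rank patients the wrong way round on exposure.

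The threshold also equals the span of a perfectly timed four-dose course, so there is no allowance for an early fourth dose. The two definitions in SAP section 2.4 differ by the one day that can decide the matter.

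At stake is how the PAS result for the primary endpoint is read. The efficacy criterion in SAP section 2.8.2.1, "If the lower bound of the exact 95% CI is greater than 15" percent, follows directly after the sentence naming both populations and is not restricted to the FAS.

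**Working it through.** **The plan's own figures.** The SAP expects about 28 HSCT-TMA patients, and its Table 1 gives 2 + 22 + 4 = 28. Clopper-Pearson limits for n = 28 have widths from 12.34% to 38.71%, and 14/28 gives 30.65% to 69.35%. These match the stated 12.3% to 38.7% and 30.6% to 69.4%.

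**Formulas.** The first dose is on Day 1.

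- Treatment period = (last dose day + 7) − 1.
- Duration of treatment = (last dose day + 7) − 1 + 1.
- In the PAS if the value is at least 28.

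**Missed doses.**

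| Doses given on Days | Doses | Treatment period | With +1 | PAS |
|---|---|---|---|---|
| 1, 8, 15, 22 | 4 | 28 | 29 | in on both |
| 1, 8, 22 | 3 | 28 | 29 | in on both |
| 1, 15, 22 | 3 | 28 | 29 | in on both |
| 1, 22 | 2 | 28 | 29 | in on both |
| 1, 8, 15 | 3 | 21 | 22 | out on both |

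The inversion of two doses in and three doses out does not depend on the day count.

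**Early fourth dose that is also the last dose.**

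| Fourth dose on Day | Treatment period | With +1 | PAS |
|---|---|---|---|
| 22 | 28 | 29 | in on both |
| 21 | 27 | 28 | out; in with +1 |
| 20 | 26 | 27 | out on both |

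A patient last dosed on Day 21 would count as treated for at least 4 weeks in the optional exposure summary (28 days) but would fall outside the PAS (27 days).

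**Stage 3.** Doses there fall on Days 29 to 50. A last dose on Day 29 already gives (29 + 7) − 1 = 35 days, so the early-fourth-dose problem does not arise for these patients.

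**Effect of one patient on the PAS rate.** At 14/28 = 50.0%, removing a responder gives 13/27 = 48.1% and removing a non-responder gives 14/27 = 51.9%. The shift is about 1.9 points either way.

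**Effect on the 15% rule.** The exact lower bound is 14.95% for 8/25, which fails, and 15.63% for 8/24, which passes. Removing one non-responder from a PAS of 25 is enough to cross the line. The size 25 is illustrative, because the documents do not give the PAS size.

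**The case against.** The strongest reply is that this is a minimum-exposure set, stated consistently in both documents, and that the FAS includes every treated HSCT-TMA patient. The SAP also plans summaries of doses received and relative dose intensity, a dosing listing, and a listing of patients who did not complete treatment. A reader could therefore spot a two-dose patient in the PAS. All of that stands. It limits the consequence but does not alter the rule.

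A reader might infer something stronger: that the PAS excludes patients who received all four doses within the allowed window. The documents do not establish this:

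- A Day 21 dose is excluded only if the day count omits the extra day.
- A Day 20 dose fails on either count, but it is within window only on one reading of protocol section 10.1.6. That sentence can equally be read as a trigger for contacting the medical monitor, or as two days beyond a visit window that is not printed for Stage 2.
- The printed ± 1 window belongs to Stage 1, which has 2 of the 28 HSCT-TMA patients.
- Only patients whose early fourth dose was their last can be affected.

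A reader might also put the effect of one misplaced patient at 1/28, or 3.6 points. In a set of 28, that is the shift from reversing one patient's response. Removing a patient moves the rate by about 1.9 points at 50%.

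Nor does it follow that agreement between the FAS and PAS is uninterpretable. It is weaker evidence about patients treated as planned than the name of the set suggests.

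**Conclusion.** The point holds. As written, the PAS can include a patient with two of four doses and exclude one with three, on either day count, and nothing else in the documents corrects this. Separately, the cut-off leaves no margin for an early final fourth dose, and for Day 21 the SAP's two definitions give opposite answers.

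The consequence is limited to the PAS analysis of the primary endpoint. The FAS result does not change, and patients who continue into Stage 3 escape the early-dose problem. The documents do not show that any patient is actually misplaced, and the number cannot be computed from them. The 1.9-point figure assumes 28 patients and a 50% response rate; the threshold example assumes a PAS of 25 with 8 responders. The SAP also does not say whether a supplemental dose given with plasma therapy counts as the last dose, so the span itself is not fully specified.

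The change should be made, but the primary FAS analysis does not depend on it.

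**What to change.** Before database lock:

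1. Define the PAS as HSCT-TMA patients who received all four initial scheduled weekly doses, in Stage 1 or Stage 2, not counting supplemental doses. Wording confined to Stage 2 would exclude the two HSCT-TMA patients in Cohort 3 of Stage 1.
2. State in the SAP any timing tolerance to be used for this analysis set. It cannot be left to visit windows, since none is printed per visit for Stage 2. The tolerance would serve to classify patients for analysis, not to direct dosing.
3. Use one day-count convention for treatment period and duration of treatment in SAP sections 2.2, 2.4 and 3.2.2.2.
4. Align protocol section 13.2.1.2 and the synopsis.

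The cost is a few sentences. Administration dates are already recorded (protocol section 10.3) and doses received are already summarized (SAP section 3.2.2.2), so no new data are needed. Protocol section 13.2 requires the SAP to be final before the interim database lock, which sets the deadline. The small downside is that the PAS may lose a few patients who missed intermediate doses.
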